This is a pilot feasibility study. We will use a randomized controlled crossover design to test the feasibility and preliminary efficacy of 40Hz music (Condition A) intervention, 40 Hz sound intervention (Condition B), and preferred music (Condition C) on cognitive function in 30 community-dwelling older adults with MCI. The participants will be randomized to three groups (n=10 in each group) with different sequences of exposure to three conditions. In each condition, participants will be instructed to listen to the assigned condition for one hour each day for 4 weeks. There will be a 10-14-day wash-out between each condition. Cognitive function, possible covariates including sleep, anxiety, depression will be collected at baseline and the end of each condition using validated measures. Qualitative semi-structured interviews will be conducted after completing each condition to understand participant's experience, preference, and acceptability of the three conditions. (Figure 1).

Recruitment: We aim to enroll 30 eligible older adults with MCI. The sample will be recruited from multiple sources including community recruitment, geriatric primary care and memory clinics affiliated with the Johns Hopkins University Health System, online recruitment. We will build upon successful recruitment strategies of the Johns Hopkins Center for Injury Research and Policy as well as the Center for Innovative Care in Aging which involves developing targeted study flyers, sending mailings by agencies and medical practices serving older adults, and working with community based advisory groups. The study flyers will be posted near the front desk and examine rooms of clinics, and the activity rooms in senior community centers; In addition, the study team will do presentations at the community center to inform residents of the research opportunity. Interested older adults will contact the research team or leave their contact information (name and phone number) and give

[figure not shown]

Figure 1: Proposed Study Procedure Chart

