Study randomization and blinding: Before enrollment, a randomization schedule in REDCap will be created using a random number generator. After baseline data collection, eligible participants will be randomized to three groups (n=10 in each group) with different sequences of exposure to three conditions. The study is a single-blind study. The data collector for outcome assessments will be blinded for participant's exposed condition.

Study duration: The total duration of the study participation will be around 18-20 weeks including 4 weeks of each condition, 10-14 days washout, and 1 week of data collection.

Number of study visits: There will be six data collection visits at the participant's home or at the School of Nursing based on the participant's preference. The 3 baseline data collections will take about 40 minutes. The 3 posttest data collections will take about 60 minutes.

Delivery of Music/Sound Interventions. Within 1 week of baseline data collection, participants will start their assigned sequence of study activity at their home. Participants will listen to the three music/sound conditions: A (40Hz music), B (Preferred Music), and C (40 Hz Sound) with their group assigned sequence (Group 1 A-B-C; Group 2 B-C-A; Group 3. C-A-B). The research team will provide a MP3 player and headphones for each participant to listen to the assigned music/sound during the study. The research team will set up the "listening station" at home with the participant before any assigned activity. Participants will sit on a comfortable chair in front of a table while listening to music/sound. The speaker will be placed on the table. Participants can move hands, stretch arms at the sitting or standing position or they can move around the table

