Condition C. Preferred music: A personalized preferred music playlist with 15-20 pieces of music will be created. We ask the participant to complete the "Assessment of Personal Music Preference"⁴⁷, provide the names of their favorite music, and select preferred music pieces from our music library during baseline data collection. To maximize participant's enjoyment and potential musical effect, a personal playlist for each participant will be created using their identified/selected music pieces and individual genre of music by the music interventionist. The study music library will be expanded as we add more participant-suggested music.

Data collection: Data will be collected before and after each condition. In total, the study includes 3 baseline and 3 posttest data collections. Data collection will take place at the participant's home or in a private room at the School of Nursing, a private room at Wald Community Nursing Center, or JHU clinical research unit per the participant's preference. Demographic and other information, and music preference will be collected at 1st baseline data collection. Cognitive function, sweat neurology biomarkers, survey on sleep, anxiety, depression data will be collected at each baseline and posttest data collection. Semi-structured interview data will be collected at each posttest data collection. The interview conversations will be audio recorded and field notes will be taken by a research team member during the interview. We estimate each interview will last about 20 minutes. The participant will be asked to answer open-ended questions about the participant's experience with the study interventions. The voice recordings will be sent to Production Transcripts for transcription (<https://www.productiontranscripts.com/>).

Measures:

Primary outcome 1: Episodic Memory will be measured using "One Card Learning" (visual)and International Shopping List, and Delayed Recall"(verbal) using Cogstate Alzheimer's Battery

(CAB). A composite episodic memory score will be calculated by taking the average of the standardized scores across the three tests

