Primary outcome 2: Global cognition will be measured using Cogstate Alzheimer's Battery (CAB), a set of rapid, reliable and highly sensitive computerized cognitive tests across a comprehensive list of cognitive domains in people with MCI and Alzheimer's disease. CAB has shown good acceptability, efficiency, and stability for the repeated assessment of cognitive function for neuro-epidemiological studies in older adults with MCI and AD. Sub-domains of global cognition in CAB are secondary cognitive outcomes of the study, which include 1) Episodic memory; 2) Executive function will be measured using Modified Groton Maze Learning Test; 3) Attention will be measured using the Identification Test; 4) Working memory will be measured using One Back Test; 5) Processing speed will be measured using "Detection Test"; calculated by following the Cogstate data analysis guidelines. Global cognition will be a composite score of these assessments calculated by following the Cogstate data analysis guidelines.

Feasibility and Acceptability measures: (1) *Study level:* the research team will track the recruitment process from each source, data completeness, and adherence of each study condition, and rate and reasons for participant withdrawal. (2) *Participant level:* We will send a Redcap survey link to each participant daily to collect data on intervention adherence and safety of the prior session (time, duration, volume of sound, any adverse events). Qualitative individual interview data will be collected after the participant completes each condition and used to understand the participant's perceptions and experience with the sound/music conditions, the possibility for long-term use of the conditions, how to build a sound intervention to their routine (best to remember to do it).

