Sample size and power: We will recruit 30-50 participants based on feasibility for recruitment and study cost estimation. With 10%-15% attrition, statistical power of 0.80, within-subject correlation (r) = 0.8, alpha of 0.05, we will be able to detect a moderate effect size (ES) of 0.5 for changes in cognitive outcomes overtime between conditions. If the ES turned out to be small, this study would provide precise ES for future efficacy trials.

Descriptive analysis will be performed to examine the underlying distributions of each outcomes measure. Distributional assumptions for the proposed statistical method will be verified and data transformation will be performed if required.

Aim 1 is to test the feasibility and acceptability of the three sound/music in older adults with MCI. Both qualitative and quantitative data will be used.

Qualitative data: we will code each transcript (naming segments of data with labels) and then use constant comparison (systematic comparisons of data with data, data with concepts, concepts with concepts, comparison within cases, and comparisons across cases). The interview guide may be revised if the findings suggest the need to include additional perspectives. We will file, index, and catalogue all data and use audit trails to trace the thinking and decision making by writing accurate and comprehensive notes and memos. Nvivo version 12 will be used to manage the interview data and field notes. Transcript of audio-recording with the filed notes will be analyzed using conventional content analysis to identify patterns, consistencies, and differences throughout the interviews.

Quantitative data: Descriptive analysis will be used to test recruitment, retention, adherence, and safety.

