Aim 2 is to determine the preliminary efficacy of A for four weeks on cognitive function, compared with B and C. Linear mixed effect (LME) models will be used to examine the change in the outcome measures over time, with the post-pre difference score as the dependent variable. LME models allow the analysis of unbalanced data. The data is considered unbalanced when the study participants have varied number of observations and the observation times differ among the study participants. The model includes condition (treatment) as a fixed effect of primary interest, and controlled for sequence (as a fixed effect) to account for potential order effects due to the crossover design. Age and sex will be included as additional covariates. A random intercept for participant is specified to account for within-subject correlation across conditions.

Treatment of Missing Data. With the use of direct data entry, we expect to minimize missing data. We will obtain reasons for the study drop-outs so that we can assess the missing data mechanism. The pattern of missingness will be examined, and baseline responses compared between those with and without missing data. Variables related to missingness will be included in the analyses, which should yield valid inferences. We will use imputation to impute missing data

and then compare the results from with and without imputation. If the assumption of missing at random is reasonable, likelihood-based methods that ignore the response mechanism will be appropriate. If the probability of missingness depends on the unobserved data even after the observed data are conditioned (i.e., non-ignorable missingness), we will consider both selection models and pattern-mixture models to guide our chosen model. The effect of our assumptions on inferences regarding the missing mechanism will be assessed using sensitivity analyses.

9. Risks

Minimal risks to study participants are expected. Subjects may experience boredom or feel the sound/music is unpleasant during the sessions. The risk is minimized as we use participant preferred music and 40 Hz music to develop the personal playlist. We will stop the assigned sound/music exposure if the participant reports that they feel uncomfortable or cannot tolerate the condition. In addition, the participant may experience psychological reactions to completing the questionnaire data and cognitive tests. Since the questions are benign, the risk is minimal.

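### The Aim 2 model relies on a sequence term that cannot act on the condition contrasts to handle order effects, and it has no period term

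*Combined protocol and SAP*

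**What the plan says.** Section 8, Aim 2, specifies a linear mixed model "with the post-pre difference score as the dependent variable". Condition is the fixed effect of interest, age and sex are covariates, and each participant has a random intercept. The model is "controlled for sequence (as a fixed effect) to account for potential order effects due to the crossover design". Neither this section nor any other names a period, visit or test-occasion term.

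Section 5 gives three cyclic sequences (A-B-C, B-C-A, C-A-B) with 10 participants planned in each. On testing, the Data collection paragraph says: "In total, the study includes 3 baseline and 3 posttest data collections". On allocation, it says that "a randomization schedule in REDCap will be created using a random number generator"; blocking is not mentioned. Under Primary outcome 2 the cognitive battery is credited with "stability for the repeated assessment of cognitive function". The power statement in Section 8 begins: "With 10%-15% attrition, statistical power of 0.80, within-subject correlation (r) = 0.8".

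**The concern.** In a crossover, the order effect that can disturb a treatment comparison is a difference between periods. Here the likely source is practice, because each participant takes the cognitive battery six times. Using the post-minus-pre score deals with part of this: a practice gain that is the same in all three periods goes into the intercept. A gain that differs between periods does not, for example one that is larger in the first pre/post pair.

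The plan gives this job to sequence, which identifies the group a participant belongs to and takes one value for all of that participant's periods. If it cannot do the job, two things are at stake. Period differences inflate the residual and cost power. When the numbers completing each sequence differ, they also bias A−B and A−C, the contrasts that answer primary objective 2.

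**Working it through.** **Inputs.** From the documents: the three sequences, 10 per group, attrition of 10-15%, r = 0.8, target effect 0.5, alpha 0.05 (taken as two-sided). I use 26 completers of 30 (four lost, 13%). Assumed, because no practice size is given: pre-to-post gains g1, g2, g3 = 0.4, 0.1, 0 in periods 1 to 3, in units of the SD of a single score, with compound symmetry for the level scores. Conditions B and C swap labels between the delivery paragraph of Section 5 and the condition descriptions in the same section. The square is balanced under either labelling, so the result is unaffected, but the labels need reconciling.

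**1. The plan's power figure.** Read r = 0.8 as the pre-post correlation. The change score then has variance 2(1 − 0.8) = 0.4, and the difference of two changes has variance 0.8. The standardized effect is 0.5/√0.8 = 0.559. A paired t-test has power 0.798 at 27 completers and 0.765 at 25, so on this reading the stated 0.80 is reached only at the favourable end of attrition from 30 recruits. Reading r as the correlation between conditions gives 0.977 at 27. Recruiting towards 50 also gives slack (0.956 at 45 completers).

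**2. What sequence does.** With complete data the A−B estimate is the mean over participants of (change under A − change under B). Anything constant within a participant cancels, and that includes sequence. Generalized least squares confirms it: with or without sequence the standard error (SE) is √(0.8/30) = 0.1633 at 10/10/10 and √(0.8/26) = 0.1754 at 26 completers, and the estimates are identical.

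**3. Bias without period.** For completers n1, n2, n3 in Groups 1, 2, 3, with N in total:

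- A−B: [n1(g1 − g2) + n2(g3 − g1) + n3(g2 − g3)]/N = (0.3n1 − 0.4n2 + 0.1n3)/N
- A−C: [n1(g1 − g3) + n2(g3 − g2) + n3(g2 − g1)]/N = (0.4n1 − 0.1n2 − 0.3n3)/N

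Both are zero when n1 = n2 = n3.

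| Completers | A−B bias | A−C bias | SE with period |
|---|---|---|---|
| 9/9/8 | −0.1/26 = −0.004 | 0.3/26 = 0.012 | 0.1755 |
| 10/9/7 | 0.1/26 = 0.004 | 1.0/26 = 0.038 | – |
| 10/10/6 | −0.4/26 = −0.015 | 1.2/26 = 0.046 | 0.1775 |
| 10/6/10 | 1.6/26 = 0.062 | 0.4/26 = 0.015 | – |
| 6/10/10 | −1.2/26 = −0.046 | −1.6/26 = −0.062 | – |
| 13/7/6 | 1.7/26 = 0.065 | 2.7/26 = 0.104 | 0.1813 |

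With period in the model every bias is zero. Over all random losses of four from 10/10/10 the mean absolute bias is 0.018. The 13/7/6 split cannot come from attrition alone; it needs uneven allocation.

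**4. Precision without period.** The gains have mean 0.167 and a sum of squared deviations of 0.0867. The within-participant residual has 2 × 26 − 2 = 50 degrees of freedom, so its expected mean square is 0.4 + 26 × 0.0867/50 = 0.445. The SE is √(2 × 0.445/26) = 0.185, against 0.175, a rise of 5.5%. The same formula gives 1.4% for halved gains (0.2/0.05/0). With later gains held at 0.1/0, it gives 3.0% for a first-period gain of 0.3 and 12.6% for 0.6.

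**5. The planned REML model, simulated** (9/9/8, with sequence, age and sex, 6,000 replicates):

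| A−B | Without period | With period |
|---|---|---|
| SE | 0.179 | 0.171 |
| Power at 0.5 SD | 0.774 | 0.807 |
| Type I error | 0.042 | 0.052 |
| Power, halved gains | 0.796 | 0.807 |

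A purely within-participant analysis agrees in direction: power 0.757 against 0.797, and type I error 0.038 against 0.049.

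**The case against.** The strongest reply is that the design already does most of the work. Each condition occurs once in each period, so with equal completed sequences the estimates are unbiased whatever the practice profile. The post-minus-pre score also removes a gain common to all periods. This is correct. What remains in that case is lost precision and a test that is conservative, not liberal.

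Second, the bias figures above treat leavers as contributing nothing, whereas the mixed model keeps their completed periods. Keeping them does lower the bias. With four participants in Group 1 or 2 lost after period 1, the largest bias is 0.030 SD, or 0.041 to 0.051 if a participant's change scores correlate 0.3 to 0.6, against 0.062. With losses spread 2/1/1 it is at most 0.007 (0.010 to 0.012 with that correlation). With partial data the sequence term does move the contrasts slightly, for example from −0.026 to −0.030, but it does not correct the bias. The completer-split figures are therefore upper-end values.

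Third, the largest figures depart from the planned 10 per group, and silence about blocking does not show that allocation will be uneven. That is fair, so 13/7/6 should carry little weight. Fifty recruits could split 17/17/16, with bias of at most 0.4/50 = 0.008 over group orders.

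Fourth, the practice sizes are assumed, the plan describes the battery as stable, and it says "This is a pilot feasibility study". All of this limits the size of the problem. It does not make the sequence term work, and Section 8 also expects the study to supply effect sizes for later trials.

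**Conclusion.** The concern holds. The plan names a safeguard against order effects that, with complete data, has no influence on the contrasts it is meant to protect. That follows from the structure of the model and needs no assumption about practice.

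The consequence is modest and does depend on assumptions. At the assumed gains and near-equal sequences, about 3 points of power are lost (0.774 against 0.807) and the test is slightly conservative. At half those gains the loss is about 1 point, and with no period difference there is none. Bias needs both unequal sequences and unequal gains. Under the planned allocation and attrition it is typically 0.01 to 0.02 SD, and at most about 0.06 SD if one group takes all the losses and leavers' data are discarded. The SE is near 0.175 and the target effect is 0.5. This would rarely change a pilot's conclusion, but it should be corrected because the statement is wrong and the repair costs almost nothing.

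**What to change.** For the primary and secondary cognitive outcomes, fit condition + period (1, 2, 3, categorical) + sequence + age + sex, with a random participant intercept. Reword the Aim 2 sentence so that period, not sequence, is named as the control for period and practice effects. Sequence can stay as a design term.

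Do not claim that this controls carryover. In these three sequences B only ever follows A, C only follows B, and A only follows C, so an effect of the preceding condition cannot be cleanly separated from the effect of the condition itself.

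The cost is one sentence of text and 2 degrees of freedom. The SE rises by 0.1% at 9/9/8, 1.2% at 10/10/6 and 3.4% at 13/7/6. If there is no practice effect, power is essentially unchanged (0.815 with period against 0.816 without, at 9/9/9).
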